5.3 Adherence Assessment

Resident and staff participants will be asked to attend the intervention visit and the training, respectively. We will assess adherence to these sessions among resident and staff participants.

5.4 Concomitant Therapy

Not applicable

5.4.1 Allowed Therapy

Not applicable

5.4.2 Required Therapy

Not applicable

5.4.3 Prohibited Therapy

Not applicable

5.5 Participant Discontinuation/Withdrawal from the Study

Participants are free to withdraw from participation in the study at any time upon request.

An investigator may discontinue a participant from the study for the following reasons:

- Unacceptable adverse event(s)
- Significant study intervention non-compliance, unless varying compliance is an aspect of the study objectives
- Lost-to-follow up; unable to contact participant (see Section 5.6 - Lost to Follow-Up)
- Any event or medical condition or situation occurs such that continued collection of follow-up study data would not be in the best interest of the participant or might require an additional treatment that would confound the interpretation of the study
- The participant meets an exclusion criterion (either newly developed or not previously recognized) that precludes further study participation

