5) Procedures for protecting against hunger. It is possible that individuals who are attempting to quit smoking may experience hunger. Should this issue arise during the intervention, we will provide resident participants a list of resources of free food including food banks for food in bulk, soup kitchens for daily meals, and other free meal programs.

6) Procedures for protecting against withdrawal symptoms. Participants may experience symptoms of nicotine withdrawal from reducing consumption or quitting smoking. These symptoms include irritability, fatigue, headaches or cravings for cigarettes. Participants who experience these symptoms will be referred to their primary care providers to obtain a prescription for nicotine replacement therapy or other medications for cessation and/or to be evaluated for contraindications to these medications. Study staff will ask participants about these symptoms during follow-up visits.

7) Procedures for handling reportable conditions. During the informed consent process, participants will be informed of information that must be reported by law should it be revealed during study visits, including suicidality and homicidality. The PI will train the study staff on how to assess for symptoms of suicidality or homicidality, and the procedures to follow in the event of these occurrences. In addition, the PI will be on call at all times and will be available for consultation.

- 8) Procedures for protecting against fatigue or boredom. The enrollment study visit will last approximately 1 hour, and the follow-up visits at 3- and 6 months (intervention and wait-list control participants) and 9- and 12-months (wait-list control participants) will last approximately a half-hour to 45 minutes. The in-depth, semi-structured interviews and focus group in Aim 3 will last 60 minutes to 90 minutes. Study staff will inform participants, during informed consent and at each study visit, that they can take breaks or stop participating in the study at any time.
- 9) Added protections for vulnerable populations. If a participant becomes incarcerated during the course of the study, they will be censored from participation during incarceration. If released from jail/prison during the study timeframe they can choose to re-enroll and a research assistant will repeat the informed consent process using procedures explained above.

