3.1 Characteristics

Overview of the intervention. The intervention, delivered by study staff includes: 1) one-on-one counseling to PSH residents who are smokers on how to adopt a smoke-free home, and 2) training for PSH staff on how to provide referrals to cessation services.

Trial design. We have chosen a cluster-randomized, wait-list controlled trial,^{75,76} where PSH sites will be randomized into intervention and wait-list control groups. Those in the wait-list control group will receive usual care first and then cross over to the intervention arm.

Setting. Study procedures will take place in a private room at each PSH site.

Study procedures for PSH resident participants. Eligible resident participants include current smokers [(smoked at least 100 cigarettes in lifetime (i.e. the standard definition for a life-time smoker), daily or non-daily smoking in the past 7 days and at least 5 cigarettes per day, verified by expired Carbon Monoxide (CO) ≥ 8 parts per million (ppm)]⁷⁷ who smoke in their homes and

expect to live in the PSH site for at least 12 months, are ≥ 18 years of age, are English proficient, and are able to provide informed consent. Study staff will advertise the study to residents the week prior to enrollment by placing flyers at the site and making announcements at community meetings. Study staff will be present at the recruitment sites during designated times to screen interested participants for eligibility, obtain written informed consent using the teach-to-goal method,⁷⁸ and enroll those eligible. **The expired CO assessment for eligibility assessment is to ensure that participants recruited are regular smokers who smoke an average of 5 cigarettes per day. To obtain a CO assessment, the participant blows into a handheld CO monitor that records the expired CO reading (Bedfont EC50 Smokerlyser; Bedfont Scientific Ltd). We considered including monolingual Spanish speaking participants in our study, however, the proportion of monolingual Spanish speaking participants is ~ 5% based on estimates from our partner organizations where the study will be conducted. Therefore, we chose to include English speaking participants in this study.**

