5.1 Administration and/or Delivery of Study Intervention

Smoke-free home PSH resident intervention. Study staff will deliver a one hour, one-on-one counseling to PSH residents that includes: (1) a step-by-step guide on how to voluntarily adopt a smoke-free home, (2) information on SHS and thirdhand smoke, alternative combustible tobacco and nicotine product use, cannabis-tobacco co-use, effects of SHS on kids and pets,⁴⁰⁻

⁴³(3) a worksheet on calculating personal costs related to tobacco use, and (4) pledges to designate one's home smoke-free.

Smoke-free home PSH staff intervention. Study staff will conduct a two-hour training for PSH staff on how to provide referrals to smoking cessation programs using materials previously developed from the UCSF's Rxforchange curriculum for service providers.⁷⁹ PSH staff play an integral role in residents' lives by facilitating access to services, whether they be mental health, substance use or healthcare services. In keeping with that model, our training is directed toward empowering PSH staff to provide referrals to local cessation services using the ask, advise, and refer approach,⁸⁰ which has been shown to increase engagement in cessation treatment. The training will address nicotine addiction, tobacco use among PSH residents, pilot data, brief cessation counseling (ask, advise, and refer), and local resources for cessation. Because PSH resident-PSH staff encounters will take place as part of routine care, we will request permission from a random sample of staff and resident dyads (n=40) to record these interactions to assess fidelity.

Usual care. The current standard of care includes no interventions for smoke-free home adoption or referrals to smoking cessation resources.

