9.3 Statistical Analysis Plans

Descriptive analyses and missing data. We will estimate means and proportions, variation, and confidence intervals for demographic and other covariates. We will consider relevant biological variables of age, sex, and race/ethnicity. We will examine patterns of smoke-free home adoption and cessation behaviors at each visit to assess whether quitting took place in the context of voluntary adoption of a smoke-free home. We will determine whether participant baseline characteristics are independent of intervention group assignment (randomization check) and attrition (attrition analysis). Missing data will be accommodated by multiple imputation.¹⁰³⁻¹⁰⁵

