9.3.2 Primary Analysis (or Analysis of Primary Endpoints)

The primary outcome is self-reported voluntary adoption of smoke-free homes for ≥ 90 days at 6 months follow-up. Primary analyses include intention-to-treat comparisons. The 3-level data structure—including PSH housing site, residents, and repeated assessments—will be accommodated by mixed logistic models with random intercepts for sites and residents. The primary outcome will be a binary indicator of adopting a smoke-free home which, in an intention-to-treat analysis, will be regressed onto indicators of experimental groups, categorical time (baseline, 3 months, 6 months), and the group-by-time interaction. Any significant intervention group main effect at follow-up and group-by-time interaction effect will be interpreted and described. If any key demographic or risk factors are imbalanced at baseline, we will include a propensity score-based adjustment.¹⁰⁶⁻¹⁰⁸

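### Section 5.5 allows removal from the study for intervention non-compliance, which before 6 months can reach only the intervention arm, and nothing secures the 6-month outcome of those removed

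*Combined protocol and SAP*

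**What the plan says.** Section 5.5 introduces its list with "An investigator may discontinue a participant from the study for the following reasons". One reason on the list is "Significant study intervention non-compliance, unless varying compliance is an aspect of the study objectives". Another covers an event or condition that "might require an additional treatment that would confound the interpretation of the study".

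On what each arm receives before the endpoint, section 3.1 says "Those in the wait-list control group will receive usual care first and then cross over to the intervention arm", and section 5.1 describes usual care: "The current standard of care includes no interventions for smoke-free home adoption or referrals to smoking cessation resources". Under section 4.2, wait-list residents are offered the intervention only after the intervention sites in their block have finished the 6-month follow-up.

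On the analysis, section 9.3.2 says "Primary analyses include intention-to-treat comparisons", and section 9.3 says "Missing data will be accommodated by multiple imputation". Section 9.3.1, on analysis populations, is marked as not applicable. Section 6.2.4 provides for follow-up after the intervention is discontinued, but the only procedure it lists is adverse event assessment.

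**The concern.** An intention-to-treat comparison needs the outcome of every enrolled resident, whatever they did with the intervention. The non-compliance reason works against this in three ways.

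- It acts at the level of the study, so it can end outcome collection as well as the intervention.
- Before 6 months it can reach one arm only, because wait-list residents have no study intervention to be non-compliant with. The trial is not blinded (4.7), so the arm is known when the discretion is used.
- It selects on a characteristic likely to be related to the outcome. A resident who misses the counseling session is unlikely to adopt more often than one who attends.

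At stake is the size of the reported effect on smoke-free home adoption, and likewise on abstinence. If low adopters leave one arm only, and their missing outcomes are filled in from residents who attended, the intervention looks better than it was across all residents enrolled at its sites.

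**Working it through.** **Step 1: can the rule reach the control arm before 6 months?** Sections 3.1, 4.2 and 5.1 together say no. For residents, the intervention is a single one-hour session (5.1), and adherence is assessed as attendance (5.3). Non-compliance is therefore largely non-attendance at intervention sites. No threshold defines when it is significant.

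**Step 2: does any section secure the outcome after removal?** None does. Section 6.2.4 lists only adverse events, 9.3.1 defines no analysis set, and 9.3 names multiple imputation without giving a model.

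**Step 3: reproduce the plan's reference figure (9.1.1).** Inputs: 400 residents, 80% retention (160 per arm), 16 residents per site at 6 months, intra-site correlation 0.077, control rate 12%, 80% power, two-sided alpha 0.05.

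- Design effect: 1 + (16 − 1) × 0.077 = 2.155 (stated 2.16).
- Effective number per arm: 160 / 2.155 = 74.2.
- Detectable intervention rate with unpooled two-proportion variance: 30.3%, as stated. A pooled variance gives 30.7%.

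The reference effect is 30.3 − 12 = 18.3 points.

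**Step 4: effect of removal, for illustration.** The documents give no removal rate. Let f be the share of the intervention arm removed, r the adoption rate those residents would have had, and p the true rate over the whole arm. If the missing outcomes are imputed from retained residents without using attendance, the arm will read about (p − f × r) / (1 − f). Assume r = 12%, the control rate, and no such removal in the control arm.

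| f | Calculation | Rate read | Effect | Overstatement |
|---|---|---|---|---|
| 0% | 0.303 / 1 | 30.3% | 18.3 points | 0 |
| 5% | (0.303 − 0.006) / 0.95 | 31.3% | 19.3 points | 1.0 |
| 10% | (0.303 − 0.012) / 0.90 | 32.3% | 20.3 points | 2.0 |
| 15% | (0.303 − 0.018) / 0.85 | 33.5% | 21.5 points | 3.2 |

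**Step 5: the same scenario with no true effect.** (0.12 − 0.12f) / (1 − f) = 0.12 for every f. There is no false difference.

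**Step 6: dependence on r.** A false difference under the null appears only if those removed would have adopted below 12%. With 10% removed and r between 0% and 6%, the arm would read 13.3% to 12.7%, a false difference of 1.3 to 0.7 points, and two-sided type I error would be 5.7% to 5.2%. These inputs are also assumptions, and they count the removals as additional to the planned 20% loss.

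**The case against.** The strongest reply is that the protocol does not remove anyone automatically and does not drop anyone from the analysis. Section 5.5 says the investigator may discontinue a resident, and its exception for varying compliance could be read as switching the rule off. Section 5.6 shows a clear intent to retain: missed visits trigger tracking where the resident has consented, and lost residents are sought so that the intervention session can be scheduled. Section 9.3 imputes missing data, and attendance is recorded, so it could enter the imputation model.

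Much of this stands. A reader might infer that the rule breaks the intention-to-treat analysis, or that imputation must repeat the bias. The documents support neither: removal is discretionary, imputation can keep removed residents in the comparison, and the imputation model is unspecified rather than known to be wrong. The reply does not close the gap, however. Varying compliance is not among the objectives in section 2, the protocol never says whether the exception applies, and an intent to retain does not cancel a written power to remove.

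A reader might also infer that the additional-treatment reason works mainly on the intervention arm and inflates the effect. That is not established. The reason covers both arms and only treatment that would confound interpretation. Prohibited therapy is marked as not applicable (5.4.3), and use of cessation aids is simply measured (7.1). Removing residents who take up cessation treatment could remove quitters or adopters, so the bias could run either way.

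Finally, the upper figures in the table suppose that all of the assumed 10% to 15% are removed. If only half were, f would be 5% to 7.5% and the overstatement about 1.0 to 1.5 points. If they would have been lost anyway within the planned 20%, the added bias is nil.

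**Conclusion.** The concern holds in a limited form. Section 5.5 permits study-level removal for a reason that, before the primary endpoint, only intervention residents can meet, and no section secures their 6-month outcome. This conflicts with the stated intention-to-treat comparison and puts it at risk. The estimate would rest on a missing-at-random assumption that is doubtful when removal depends on compliance. If attendance is not in the imputation model, the effect would tend to be overstated.

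The size is unknown. Under the stated assumptions (0% to 15% removed, adoption among them at 12%, none removed in control, attendance not modelled), the overstatement is 0 to 3.2 points on an effect of 18.3. That scenario exaggerates a real effect and does not create a false one.

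The additional-treatment reason is a separate inconsistency. Section 1.4 says that participants with withdrawal symptoms "will be referred to their primary care providers to obtain a prescription for nicotine replacement therapy", and 9.3.3 treats use of referrals as a possible mediator of the effect, yet 5.5 could be read as allowing removal on such grounds. The passages disagree, and no direction of bias can be claimed.

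**What to change.** - Amend 5.5 to say that intervention non-compliance does not end outcome follow-up. The 6-month interview and CO reading are still sought, and the air nicotine monitor where the resident falls in the sample of about half. Leave the other discontinuation reasons in place.
- Bring 6.2.4 into line, so that follow-up after the intervention is discontinued includes the 6-month outcomes.
- Replace the entry in 9.3.1 with a defined set: all enrolled residents, analysed in the arm allocated to their site.
- In 9.3, include session attendance in the imputation model, and add a sensitivity analysis that counts missing 6-month outcomes as not smoke-free and not abstinent.
- Reconcile the additional-treatment reason in 5.5 with the referral text in 1.4 and the mediator analysis in 9.3.3.

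The cost is protocol wording, a few more 6-month visits that are already in the schedule, and one extra analysis. The design figures (400 residents, 30.3% against 12%) do not change.

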5.6 Lost to Follow-up

A participant will be considered lost to follow-up if he or she fails to return for any scheduled visits after their last visit in the study, and study staff are unable to contact the participant after at least 3 attempts. Before a participant is deemed lost to follow-up, the investigator or designee will make every effort to regain contact with the participant (where possible, 3 telephone calls and, if necessary, a letter to the participant's last known mailing address or local equivalent methods). These contact attempts will be documented in the participant's study file. Should the participant continue to be unreachable, he or she will be considered to have withdrawn from the study with a primary reason of lost to follow-up.

We will employ techniques for tracking participants that we have used in past studies to maintain high rates of follow-up: these include monthly face-to-face or telephone check-in visits and locating participants lost to follow-up.^{14,35,45-50,102} Participants will be incentivized \$5 for each monthly check-in visit, in between study visits. At enrollment, we will ask participants to provide as many forms of contact information as possible including names of family/friends and case managers, telephone numbers, addresses of places where they usually stay or can be found, and to update this information monthly. At the enrollment visit, study staff will request consent to contact participants to remind them about upcoming study visits via cellphone. If participants miss any visit (scheduled study visit or check-in) and the participant has consented to it, study staff will conduct participant tracking. Tracking involves study staff calling people whose name and contact information the participant has given the study staff for this purpose ("contacts"). Staff, when calling on these contacts, will request help in locating the participant and/or will leave a message for the participant. Study staff will tell contacts only that the participant is enrolled in a research study. If the participant has given permission to do so, the study staff may go to look for the participant at a place where the participant has said that he/she frequents. When doing this, the staff may bring along a picture of the participant to assist in locating the participant. With these follow-up procedures, we have achieved rates of retention >85% for longitudinal studies with homeless and PSH participants.⁴⁵⁻⁵⁰ **In our pilot smoke-free home intervention study, we achieved retention rates of 86% and 84% at 3- and 6-months follow-up.¹⁴**

We have developed a retention plan to facilitate recruitment/enrollment/ retention and acceptance of the study protocols. Our experience supports our estimates of retention rates of 80% at 6 months. Our 24-point culturally tailored plan includes:

- 1. Trained project staff experienced in working with populations that have experienced housing instability or homelessness, who are acutely aware of**

- racial/ethnic disparities, and are familiar with fieldwork locations in PSH** (study staff, navigators).
2. **Staff training in cultural competency regarding racial/ethnic disparities**, culturally-responsive clinical research practices, and HIPAA.
 3. A **Certificate of Confidentiality** obtained from NIH to protect the privacy of participants against most legal discovery requests and to address patients' concerns with privacy due to immigration status or legal repercussions.
 4. Offer participants the option of **meeting at their preferred** time to complete follow-up assessments (e.g., after work, after school, on the weekends) and at a location of their preference in their community (e.g., outdoor locations).
 5. Use of **personalized and culturally sensitive mailings** such as birthdays cards and holiday cards to ensure that patients feel like they are part of our study.
 6. **Community Advisory Board** to include mostly persons with lived experiences of housing instability and living in PSH, housing staff, community members, key homelessness and housing policy makers, and local tobacco control experts who will review and advise on all study stages including intervention and assessment materials (meeting 2x/year).
 7. A study design **grounded in the local culture** based on housing input, housing needs, and experience with providing services to low-income residents in PSH.
 8. Conduct **reminders** (calls/text-messages/e-mails) one week and 24 hours before the brief intervention visit and research assessments. This is to remind participants with busy schedules.
 9. Have an **international toll-free number** for participants to contact us and call in for coaching sessions, even if they travel outside the United States.
 10. **Monetary incentives** to complete the baseline (\$20), and follow-up assessments at 3-months (\$15) and 6-months (\$25), and an additional \$5 for placement of the air nicotine monitor.
 11. **Use of existing procedures to locate patients lost-to-follow up**, including working with housing staff to identify participants so that study staff can meet them at the PSH site to conduct or schedule the research assessment or schedule the intervention session; and obtaining the updated contact information for study participants and their designated contact person.
 12. **Locator Guides** with contact information for the participants, emergency contacts, friends and medical providers.
 13. Conduct **Monthly Interim Re-Contact** calls that are incentivized (\$5 visit) for participants at months in between scheduled visits to thank them for participating, remind them of the study incentives, update Locator Guides, and address any questions.
 14. Supportive telephone tobacco-use/wellness **health coaching** designed partially for participant retention. Follow-up and re-contact efforts for intervention sessions will include weekly written letters or e-mail, followed by telephone calls (three weekly attempts will be made before shifting to monthly contacts).¹³⁰
 15. Study instruments and intervention materials designed to meet the **literacy needs** of persons with low educational attainment.
 16. **Update participant contact information** in Locator Guides at follow-up assessments, coaching sessions, and interim re-contact calls.
 17. Extra effort **tracking participants lost to follow-up** at homes, shelters, outdoors using paid navigators who had lived experiences of housing instability and living in PSH.

18. Provide patients **\$5 for each telephone session**, or yoked re-contact session to defray cost of cell phone minutes.
19. Designated **tracking/scheduling staff**.
20. Use of laminated **appointment study business cards** with study contact information.
21. Collect **agency contact information** from patients where they might receive social services.
22. **Study Website** with educational materials, community resource links, and contact information for study staff.
23. Making **“home visits” in PSH and/or outdoor locations** for difficult-to-find patients.

6 Study Procedures and Assessments

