4.2 Recruitment Methods

Recruitment schedule. We will recruit 400 PSH resident participants, with 200 each in the intervention and wait-list control arms (~20 participants per site; Figure 6, Table in Recruitment and retainment section in human subjects). Within each site, all resident participants will be informed about the study and invited to participate. We will recruit participants within blocks of four housing sites per month, with each block containing two intervention and two wait-list control sites, and anticipating roll-out of one such block per month. We anticipate completing recruitment and enrollment of all participants in 6 months, allowing for a one-to-two-month extension to complete these activities. We will offer the intervention to the wait-list control participants once all participants in the intervention sites from the same block have completed their 6-month follow-up. We expect to enroll 100 PSH staff. We will obtain information on the total number of residents and staff at each site to provide an estimate of the proportion enrolled in the intervention.

Within each site, study staff will advertise the study to residents the week prior to enrollment by placing flyers at the study site and making announcements at community meetings. After the informational meeting, study staff will be present at the recruitment sites during designated times to screen interested participants for eligibility and enroll those eligible into the study. Study staff will describe the purpose of the study, the study procedures, including risks and benefits, and obtain written informed consent using the teach-to-goal method at the time of eligibility.⁷⁸ Participants will complete the baseline questionnaire and will receive the study staff-delivered intervention within one week of enrollment. We have adjusted the timeline for recruitment, intervention delivery and follow-up to account for extra time that we may need to complete study procedures to follow protocols around social distancing that PSH sites may have put in place due to COVID-19.

Data collection reimbursements. We will reimburse all resident participants with [REDACTED] gift cards for completing the baseline questionnaire, [REDACTED] the 3-month questionnaire and [REDACTED] the 6-

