6.2.2.4 Visit 4 (Months 12 to 20)

- Adverse Events assessment
- Protocol-specific assessments/procedures for waitlist control group (6-month follow-up)

6.2.3 End of Study Intervention / Visit 5

- Placement of the air nicotine monitor (6 month follow-up)
- **Air nicotine assessment procedures.** At 6 months follow-up, we will chose a random sample of participants in the intervention and waitlist control groups, approximately 50% of the sample (N=200), stratified by those reporting a smoke-free home for ≥ 90 days, < 90 days, and not at all to validate self-reports of adoption using passive air nicotine monitoring. These monitors which include a plastic container that contain a sodium bisulfate-coated filter will be purchased from and analyzed via gas chromatography by

the UCSF Helen Diller Family Comprehensive Cancer Center Tobacco Biomarkers Core.¹⁰¹ Staff will obtain permission at the time of informed consent to place monitors in residents' rooms for 7 days,³² within one week of completion of the 6-month interview. Monitors will be placed at least 1 foot away from windows, corners of the room, and exits.³² We will use a threshold of $\leq 0.9743 \mu\text{g}/\text{m}^3$ (sensitivity=69.5% and specificity=81.2%) for a home to be smoke-free.³²

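### The protocol does not say which arm gets telephone tobacco coaching, and wait-list crossover is not tied to wait-list residents' own 6-month assessments

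*Combined protocol and SAP*

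**What the plan says.** **Intervention and control.** Section 5.1 defines the resident intervention as a single one-hour, one-on-one session with four components, alongside a two-hour training for housing staff. Telephone coaching is not among the components. On usual care it says: "The current standard of care includes no interventions for smoke-free home adoption or referrals to smoking cessation resources".

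**Retention plan (Section 5.6).**
- Item 9 provides a toll-free number "for participants to contact us and call in for coaching sessions".
- Item 14 offers "Supportive telephone tobacco-use/wellness" health coaching, "designed partially for participant retention".
- Item 16 lists coaching sessions separately from interim re-contact calls.
- Item 18 pays $5 for each telephone session "or yoked re-contact session to defray cost of cell phone minutes".

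None of these items names an arm.

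**Crossover.** Section 4.2 and the Abstract offer wait-list residents the intervention "once all participants in the intervention sites from the same block have completed their 6-month follow-up", and the roll-out table in Section 4.2 follows the same order. For staff at wait-list sites, the Abstract uses a similar trigger without the block limit. Section 6.2.2.2 gives the wait-list intervention at Visit 2, the 6-month visit.

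**Air nicotine monitor.** The text under Section 6.2.3 (Visit 5) says the monitor stays in the room for 7 days, is placed within one week of the 6-month interview, and serves to validate self-reported adoption.

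**The concern.** The trial's contrast is one counselling session plus staff training against nothing. Repeated telephone contact about tobacco use would change that contrast, and the protocol leaves open how.

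- If both arms receive coaching, controls are partly treated and the comparison is pulled toward no effect.
- If only the intervention arm receives it, the estimated effect belongs to a package that Section 5.1 does not describe.

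The crossover rule is a second, smaller problem. Nothing in the trigger requires a wait-list resident's own 6-month assessment to be finished before counselling or staff training reaches the site. A resident seen late could be counselled, or live where staff are already trained, before answering the 6-month questions. Even a resident interviewed on time can be counselled at that visit and have the home monitored afterwards, so the monitor would be checking a report given before counselling against air sampled after it.

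**Working it through.** **1. The plan's own figure.** Inputs from Section 9.1.1: 400 residents, 80% retention (160 analysed per arm), 16 per site, intra-site correlation 0.077, control rate 12%, two-sided alpha 0.05, 80% power.

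- Design effect: 1 + 15 × 0.077 = 2.155.
- Effective number per arm: 160 / 2.155 = 74.2.
- Smallest detectable intervention rate with unpooled variance: 30.3%, as stated in the plan. (Pooled variance gives 30.7%.)

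**2. Coaching: illustration only.** Let f be the assumed share of controls who gain the full designed effect before their 6-month visit. The control rate becomes 0.12 + f × 0.183, since 0.303 − 0.12 = 0.183. Power is Φ(d/SE − 1.96), with d = 0.303 − control rate and SE = √[(0.303 × 0.697 + pc(1 − pc)) / 74.2], where pc is the control rate.

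| f | Control rate | d | SE | Power |
|---|---|---|---|---|
| 0 | 12.0% | 0.183 | 0.0653 | 80% |
| 10% | 13.8% | 0.165 | 0.0667 | 69% |
| 20% | 15.7% | 0.146 | 0.0680 | 58% |
| 30% | 17.5% | 0.128 | 0.0692 | 46% |

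With pooled variance the same row order gives 78.5%, 68%, 56% and 45%. For 7-day abstinence (12.6% against 4%, 160 per arm, correlation zero, pooled variance) it gives 80%, 69%, 57% and 45%. The documents give neither a coaching effect nor a share exposed, so f is unknown.

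**3. Crossover: who could be reached early.** A block has two sites per arm, so 2 × 16 = 32 retained residents per arm. Assume enrolment is spread evenly over one month with the same timing in both arms. A given wait-list resident then reaches month 6 after the last of 32 intervention residents with probability 1/33 = 3.0%, or about 5 of 160. Simulation under other assumed timings:

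| Wait-list enrolment lag | No visit delays | Delays averaging half a month in both arms |
|---|---|---|
| None | 3% | 3% |
| Quarter month | 28% | not run |
| Half month | 53% | 8% |
| One month | 100% | 21% |

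Exposure more than 3 months before the resident's own visit occurred in 0% to 0.06% of cases. A home must be smoke-free for at least 90 days to count for the primary outcome, so late crossover can hardly produce one. It can reach a 7-day abstinence measure and self-report in general.

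**4. Crossover: the monitor.** Placement up to day 7 after the interview plus 7 days of sampling extends to day 14. The sample is stratified by what residents report at 6 months, so sampling follows the interview. If a control is counselled at that same visit, the sampled days come after counselling.

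**The case against.** **On coaching.** No rule states that wait-list residents receive it. Item 18's yoked alternative suggests coaching for some and matched contact for others, item 14 speaks of re-contact for intervention sessions, and item 13 gives the monthly calls a largely administrative agenda. A reader might therefore infer that controls are certain to be treated, and the documents do not support that. What stands is that no passage assigns the arms. If the yoked reading is right, the difficulty moves to an undescribed co-intervention.

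**On crossover.** The intended order is visible. Section 3.1 says usual care comes first. Section 6.2.2.2 lists assessments before wait-list administration. Section 7.1 defines months 9 and 12 as 3 and 6 months after the intervention, and Section 9.3.3 measures wait-list change from month 6 to month 12. This largely answers any claim that the plan means to treat controls early. It does not supply the missing condition, and it does not protect the monitor, which follows the interview.

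**On the monitor's visit.** A reader might take the Visit 5 heading to mean that monitoring happens after month 12. The text under it ties placement to the 6-month interview, so the heading is a misfiling. The measure is also exploratory (Section 2.3).

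**On the trigger read literally.** One might argue that, with 80% retention, every resident in a block will almost never complete follow-up. That would delay crossover, not cause early exposure, and Section 5.6 treats unreachable participants as withdrawn.

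**Conclusion.** The point holds as two unresolved conflicts in the text.

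- **Coaching** is the more serious. It could run through all six months and so could affect the primary outcome. As written, the protocol permits either partly treated controls or an intervention arm that receives more than Section 5.1 describes. The fall in power from about 80% to 69%, 58% or 46% is a scenario resting on an assumed share of controls who gain the full effect; it does not estimate what will happen, and it does not apply to crossover.
- **Crossover** is a gap in wording with limited reach: 7-day abstinence, self-report, the monitor validation and exposure through staff training. It has almost no route to the ≥90-day outcome. The share exposed depends on enrolment and visit timing that the documents do not give.

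The plan's sample-size figures reproduce and are not in question. A reader might also infer that coaching is left out of the Aim 2 costing. The documents give no costing method or inputs, so that cannot be said.

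**What to change.** 1. Reconcile Section 5.1 with items 9, 14, 16 and 18 of Section 5.6. Either retention contacts before the 6-month outcome follow one script in both arms with no tobacco content, or coaching is listed in Section 5.1 as a component for the intervention arm only.
2. In the Abstract and Section 4.2, including the roll-out table, start resident counselling and staff training at a wait-list site only after that site's own 6-month interviews and 7-day monitors are completed or closed out. Align Section 6.2.2.2 with this.
3. List the air nicotine monitor under the 6-month visit (Visit 2).

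These are changes of wording and need no added data collection. The costs are that crossover at a wait-list site may start a few weeks later, and that any retention benefit of coaching among controls is lost.
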